5.6 Duration of Follow-up

For this protocol, all patients, including those who discontinue protocol therapy early, will be followed for response until progression, even if non-protocol therapy is initiated, and for survival for 5 years from the date of randomization. All patients must also be followed through completion of all protocol therapy.

6. Measurement of Effect

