6. CT of the chest, abdomen and pelvis. If only MRI of the abdomen and/or pelvis is available, this can be substituted for CT of the abdomen and/or pelvis but CT of the chest should still be obtained. Contrast agents should be administered unless otherwise contraindicated. PET-CTs can be used, so long as the CT portion is of the same diagnostic quality and includes IV and oral contrast. The same screening technique used at baseline should be used for all subsequent follow-up scans. Even though dosing schedules are different in the two treatment arms, radiographic imaging should be obtained every 8 weeks by calendar while on protocol treatment.
7. Submit as outlined in Section [11](#). Mandatory diagnostic tumor tissue must be submitted for central diagnostic review and classification and ancillary laboratory research studies. Peripheral blood is to be submitted per patient consent. Submit to within 4 weeks following randomization.

Rev. Add3

8. Baseline and subsequent imaging studies should be submitted to the IROC Imaging Core Facility for central image banking < 4 weeks after each imaging time point. In addition to the CT/MRI scans, baseline and subsequent [¹⁸F]-FDG PET scans, ⁶⁸Ga-PET scans and octreotide scans, if performed, should be submitted.
9. After completion of protocol treatment, monitor for adverse events for 30 days following discontinuation of treatment. Monitoring for survival, and scans should be performed every 3 months until patient is 2 years from randomization. Monitoring for survival and scans should be completed every 6 months if patient is 3-5 years from randomization. Once the patient progresses, adverse event assessments and scans no longer need to be performed but patients should be followed for survival (every 3 months until 2 years from randomization, every 6 months if 3-5 years from randomization).
10. Adverse Events Assessment is required 30 days after last dose of protocol therapy.
11. Note this is only required for patients randomized to Arm A.
12. Repeat coagulation studies only need to be followed in patients on anti-coagulant therapy and may be obtained within a +/- 3 day window along with serum electrolytes and liver function studies.
13. Baseline physical exam should be performed within 14 days of randomization.

8. Drug Formulation and Procurement

Capecitabine, temozolomide, cisplatin and etoposide will all be obtained commercially.

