9.2 Revised statistical plan after Spring 2019 DSMC recommendation (July 2019)

Sample size with power justification

Accrual on this study has been lower than expected, averaging 1-2 patients per month. The ECOG-ACRIN DSMC reviewed this study in Spring 2019 and made the recommendation to modify the statistical plan to reduce the required power of the study to 80% in order to achieve a more realistic sample size and timeframe. Therefore, a total of 80 patients will now be the accrual target to achieve 78 randomized eligible cases. The study seeks to establish an improvement in the primary endpoint, which is defined as a 67% improvement in median progression-free survival (PFS) from 6 months in the control arm (Arm B) to 10 months in the experimental arm (Arm A). The study is now designed to have 80% power for this 40% reduction in the hazard rate with 71 PFS events at full information which is now expected to occur after 75 months of accrual and 7 additional months of follow-up. The primary comparison remains a log-rank test at a one-sided significance level of 0.10. Under exponential distributions the hypothesized reduction corresponds to 1-year progression-free survival of 44% in Arm A versus 25% in Arm B.

Analysis plan including plans for formal interim analysis

The primary analysis set will include all randomized eligible patients. Progression-free survival (PFS) is defined as time from randomization to documented progression or death without progression. Patients without documented progression or death reported will be censored at the time of the last documented disease evaluation. In the secondary analyses, overall survival (OS) is defined as time from randomization to death from any cause, censoring cases who are alive at the date of last contact. Kaplan-Meier estimates will be used for event-time distributions. PFS and OS by arm will be compared using one-sided stratified log-rank tests. Stratified Cox's proportional hazards models will be used to estimate hazard ratios. Response rate (complete response or partial response) and toxicity are also secondary endpoints. Response rate will be analyzed using a Fisher's exact test at a one-sided significance level of 0.10.

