10.1 Standard-of-Care Imaging Time Points and Minimum Preferred Phases

- 10.1.1 All standard-of-care imaging studies (including CT, MRI, ⁶⁸Ga-PET scans, [¹⁸F] FDG-PET, perfusion CT, octreotide scan or any combination) of the chest, abdomen and pelvis including all phases completed will be submitted to the ACR Imaging Core Laboratory per Section [10.2](#) instructions.
- 10.1.2 Standard practice imaging studies for the trial per EA2142 procedures include:
 - Pre-treatment baseline scan for eligibility assessment.
 - Imaging studies during study-prescribed treatment—(e.g. CT scans or MRIs at every 8 week intervals).
- 10.1.3 Three-phase contrast-enhanced CT acquisition as outlined below is recommended.
 - Late arterial phase through the abdomen;
 - Portal venous phase through the abdomen and pelvis;
 - Delayed (equilibrium) phase through the abdomen at 3-4 minutes after contrast administration;
 - If performed per standard institutional practice, optional perfusion CT sequences of an area of interest may be performed if available at the participating institution.

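### Does the move from 8-week scans on treatment to 3-monthly scans afterwards bias the PFS comparison, and must Section 9.2 plan for it?

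*Combined protocol and SAP*

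**What the plan says.** All of the following is in the combined protocol and SAP.

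- **On treatment.** Section 7.1, footnote 6, applies to both arms despite their different cycle lengths: "radiographic imaging should be obtained every 8 weeks by calendar while on protocol treatment". Section 10.1.2 ties the 8-week interval to treatment in the same way: "Imaging studies during study-prescribed treatment".
- **After treatment, no progression.** Section 7.1, footnote 9: "Monitoring for survival, and scans should be performed every 3 months until patient is 2 years from randomization", and then "Monitoring for survival and scans should be completed every 6 months if patient is 3-5 years from randomization".
- **Early stoppers.** Under Section 5.6 all patients "will be followed for response until progression, even if non-protocol therapy is initiated".
- **Endpoint and censoring.** Section 9.2: "Progression-free survival (PFS) is defined as time from randomization to documented progression or death without progression". It adds: "Patients without documented progression or death reported will be censored at the time of the last documented disease evaluation".
- **Test.** Section 9.2: "PFS and OS by arm will be compared using one-sided stratified log-rank tests". Hazard ratios come from stratified Cox models. No sensitivity analysis for assessment timing is listed.

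Section 6.1 (8 weeks) and the opening of Section 10 (two months) give the imaging interval without limiting it to the treatment period.

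**The concern.** Progression is seen only when someone looks. Footnote 6 shows that the authors wanted equal looking in both arms, but that equality lasts only while patients stay on treatment. Early stoppers remain in the PFS analysis on a sparser schedule.

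The arms are different regimens with different stopping wording. Section 5.3.1 lets Arm A patients drop one agent and continue the other. Section 5.3.4.1 requires Arm B patients to stop after a platinum delay of more than 21 days, although Sections 5.3.4 and 5.3.5 also contain single-agent wording for Arm B. Unequal stopping is therefore plausible.

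More stopping in Arm A would flatter temozolomide and capecitabine and raise the false-positive rate. More stopping in Arm B would cost power. PFS is the primary endpoint, with 71 events and one-sided alpha 0.10, and a borderline result would invite the question.

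**Working it through.** **1. The design figure.** Inputs from Section 9.2: hazard ratio 0.60, one-sided alpha 0.10, power 80%, 71 events, 39 eligible per arm, medians 10 and 6 months, 75 months of accrual plus 7 of follow-up.

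- Events needed (Schoenfeld): 4 × (1.2816 + 0.8416)² / (ln 0.60)² = 69.1, so 70. With 71 events, power = Φ(√71/2 × 0.5108 − 1.2816) = Φ(0.871) = 80.8%.
- Expected events: the probability of an event by month 82 is 1 − (e^(−7λ) − e^(−82λ))/(75λ), with λ = ln 2/median. This is 0.882 in Arm A and 0.949 in Arm B, so 39 × (0.882 + 0.949) = 71.4.

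The plan's figures reproduce, and the scan rule does not enter them.

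**2. Delay per patient.** The mean delay in detection is half the scan interval. At 8 weeks it is 28/30.44 = 0.92 months; at 3 months it is 1.50 months. The difference is 0.58 months for a progression that occurs after an early stop.

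**3. Rough size under the null.** The stopping rates are assumptions. Take a constant stopping hazard with 10% stopped by 6 months in one arm and 50% in the other, if progression-free, and a 6-month median PFS in both.

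- Share stopping before an event = μ/(μ + λ), with λ = ln 2/6 = 0.1155. For 50%, μ = 0.1155 and the share is 50%. For 10%, μ = 0.0176 and the share is 13%.
- Shift in mean recorded PFS: (0.500 − 0.132) × 0.58 = 0.21 months, against a mean PFS of 6/ln 2 = 8.66 months. That is 2.5%.
- Shift of the test statistic: ln(1.025) × √71/2 ≈ 0.10. Null rejection becomes Φ(−1.28 + 0.10) = 11.9% or Φ(−1.28 − 0.10) = 8.3%, depending on which arm stops more.

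**4. Simulation.** Common set-up: 39 per arm, exponential PFS, unstratified log-rank test at one-sided 0.10. The rows differ in how stopping and scan dates are modelled. Stopping is Arm A/Arm B.

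| Assumption | Null rejection, Arm B stops more | Null rejection, Arm A stops more |
|---|---|---|
| No early stops (reference) | 10.2–10.7% | same |
| 10/50 or 50/10, scans on exact dates | 8.7–9.1% | 11.6–11.7% |
| Same, stops only in months 0–6 or 1–8 | 9.4–9.6% | 11.0–11.3% |
| 10/50 or 50/10, dates scattered ±3 days | 7.8–8.4% | 12.4–13.2% |
| Same scatter, half of progressions found through symptoms | 9.0–9.4% | 11.4–11.8% |
| Fixed proportions stopping in months 1–4 or 1–8: 15 v 30, 15 v 45, 10 v 60% | 8.7–10.7% | 10.7–11.2% |

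Monte Carlo standard error is about 0.5 point at 4,000 replicates (the last row) and 0.15 point at 40,000.

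- Equal stopping at 30/30: type I error 10.3%, the same as with no stops; power falls by 0.2 to 0.4 point.
- Power at 10/50: 79.6% falls to 75.5–76.5% with scattered dates, and 79.4% to 77.2% with exact dates.
- Outer bound, with every patient in one arm stopping at months 1–4 and none in the other: 14.8% if that arm is A, 7.0% if it is B.

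**5. What drives the upper end.** The larger shift depends on scattering scan dates over the window that Section 7.1, footnote 2, permits, which breaks ties at common scan dates. It also needs constant-hazard stopping, so that 50% stopped by 6 months becomes 75% by 12 months. And it needs no progression to be found between scheduled scans, although Section 6.1.4.4 asks sites to try to document objective progression after treatment stops and the Section 7.1 calendar keeps history and examination after treatment.

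**The case for a change.** The best case for changing the plan is that pre-specification is cheap. Section 1.7 says a later phase III trial is unlikely and that these results could change practice, so a timing check fixed before the result is known would carry more weight than one chosen afterwards. An interval-censored proportional-hazards model with a piecewise-exponential baseline held its type I error at 10.5–10.8% in simulation under unequal stopping, where the log-rank test ranged from 8.0% to 13.4%.

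Part of this stands. The mechanism is real, Section 9.2 is silent on it, and a check named in advance is more persuasive than one added later.

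The model is a weaker remedy than it looks. It is parametric, and its cut points have no basis in the documents. When half of progressions were found through symptoms, it over-corrected. At 10/50 the log-rank test moved from 10.1% to 9.0%, while the model moved from 10.5% to 11.4%, an error of similar size in the anti-conservative direction. At 50/10 it did better: 10.5% to 10.0%, against 10.1% to 11.2% for the log-rank test. A disagreement with the primary result could reflect model misfit, symptom-triggered scans or scan timing, and the analyst could not tell which.

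**Conclusion.** No change is needed. The documents contain no between-arm difference in the scan rule: one schedule serves both arms, the calendar basis removes the cycle-length effect, and Section 5.6 keeps early stoppers under assessment to progression. Less frequent imaging off treatment is a fair trade-off.

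The bias needs strongly unequal stopping before progression, for which the documents give no rates and no direction. At an assumed 10% against 50% by 6 months, the one-sided 10% error shifts by about 1 to 1.5 points with scans on their dates or with some symptom-triggered detection. It shifts by up to about 3 points with scattered dates and no such detection. Equal stopping leaves it at 10%.

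The stratified log-rank and Cox analysis is sound as written. If the arms do stop unequally, analysts can tabulate stops before progression and actual scan intervals by arm, because the Section 7.1 calendar already requires post-treatment tumor measurements and radiographic studies. They may report an interval-censored analysis beside the primary one. The unqualified intervals in Section 6.1 and at the start of Section 10 are a looseness of wording; the footnotes to Section 7.1 are the specific rule and settle the reading.

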8.1 Capecitabine

8.1.1 Other Names

Xeloda

8.1.2 Classification

Cytotoxic chemotherapy, anti-metabolite

8.1.3 Mode of Action

Capecitabine is a fluoropyrimidine carbamate that is an orally active prodrug of 5-fluorouracil. Normal cells, as well as tumor cells, metabolize 5-fluorouracil into 5-fluoro-2'deoxyuridinemonophosphate (FdUMP) and 5-fluorouridine triphosphate (FUTP). Both are metabolites that cause cell injury by two different mechanisms. FdUMP and the folate factor, N5-10-methylenetetrahydrofolate, bind to thymidylate synthase (TS) to inhibit the formation of thymidylate. This deficiency of thymidylate causes cell cycle division to halt. This is because thymidylate is necessary for thymidine triphosphate production, which is essential for DNA synthesis. FUTP works by incorporating itself into transcription in place of uridine triphosphate therefore interfering with RNA transcription and protein synthesis.

8.1.4 Storage and Stability

Capecitabine is supplied as biconvex, oblong film-coated pills, available as 500 mg pills (peach). Capecitabine is stored at 25 degrees C, with excursions permitted to 15 to 30 degrees C.

8.1.5 Dose Specifics

750 mg/m² orally by mouth twice daily on days 1-14 (Arm A)

The calculated total daily dose by body surface area (BSA) will be rounded down to the nearest 500 mg to allow doses using 500 mg pills.

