5.1.1.1 Arm A Treatment Notes

Monitor CBC and platelet count prior to drug administration.

- The calculated total daily capecitabine dose by body surface area (BSA) will be used and treatment should be administered according to the following table Only 500 mg tablets will be used:

Dose: 750 mg/m ² every 12 hours (or 1500 mg/m ² /day)		500 mg tabs	
Surface Area (m ²)	Total Daily Dose (mg)	# tabs in AM	# tabs in PM
1.2-1.5	2000	2	2
1.51-1.83	2500	3	2
1.84-2.16	3000	3	3
2.17-2.5	3500	4	3
2.51-2.83	4000	4	4

- Capecitabine should be taken morning and night, with at least 12 hours (+/- 2 hours) between each dose. Capecitabine pills should be swallowed with water within 30 minutes after a meal. Capecitabine pills may not be crushed. Capecitabine missed doses will not be made up and patients should not double-up on missed doses during treatment.
- The temozolomide dose will be capped at 400 mg daily. The calculated dose by BSA will be rounded to the closest mg amount permitted within the confines of available pill sizes. Temozolomide should be taken by mouth at night after fasting from solid food for two hours. Temozolomide capsules must not be crushed and must be administered whole. Temozolomide missed doses will not be made up and patients should not double-up on missed doses during treatment.

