5.3 Dose Modifications

5.3.1 General

Dose reductions will be based on current dose. If dose reduction is required, reduction is permanent. Missed doses will not be made up. No dose escalation is permitted for any of the study drugs.

Dose will be modified for all drugs if there is $\geq 10\%$ change in patient's weight while on study. For oral agents, particularly capecitabine, a new dose calculation may result in the same number of pills to be administered due to rounding issues.

Doses will be determined according to (1) non-hematologic AEs during the previous cycle, as well as (2) the lowest ANC and platelet counts during that cycle.

Patients may receive **a maximum of two** dose reductions per agent. If a third reduction is required, the patient should discontinue all protocol treatment. However, for Arm A, patients may discontinue one agent due to toxicity and continue the other on-study.

If different percentages of dose reductions for a specific drug are required because of two different types of toxicities, the greater percentage dose reduction should be undertaken.

AEs determined to be unrelated to study treatment will not require dose reduction.

NOTE: If patients have been off study treatment ≥ 4 weeks of next planned cycle start date, patients must discontinue protocol treatment.

NOTE: Starting cycles early is prohibited due to safety purposes.

All toxicity grades below are described using the NCI Common Terminology Criteria for Adverse Events (CTCAE) version 4.0.

All appropriate treatment areas should have access to a copy of the CTCAE version 4.0. A copy of the CTCAE version 4.0 can be downloaded from the CTEP website (<http://ctep.cancer.gov>).

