5.3.2 Capecitabine Dose Modifications

Capecitabine will be initiated at 750 mg/m^2 orally twice daily $\times 14$ days on a 28-day treatment cycle. Dose should be calculated as a total daily dose of 1500 mg/m^2 , then divided into two doses.

For all capecitabine dose modifications, if the protocol indicated that the dose should be reduced for subsequent administrations, a reduction of at least 500 mg (of the total daily dose) should be implemented even if the calculation including the dose reduction results in the same number of pills as was originally administered (example: if treated originally at 2500 mg daily, only 2000 mg daily may be administered if a dose reduction was called for).

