8.2.5 Dose Specifics

200 mg/m² by mouth once daily on days 10-14 (Arm A)

The temozolomide dose will be capped at 400 mg daily and is available as 5, 20, 100, 140, 180, or 150 mg capsules. The calculated dose by body surface area (BSA) will be rounded down to minimize the number of pills required.

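### Sections 5.1.1.1 and 8.1.5 round the Arm A capecitabine dose by different rules, which give doses 500 mg/day apart at 79 of the 164 BSA values in the dosing table

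*Combined protocol and SAP*

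**What the plan says.** Section 5.1.1.1 (Arm A Treatment Notes) states the capecitabine dose as 750 mg/m² every 12 hours ("or 1500 mg/m ² /day") and says "treatment should be administered according to the following table Only 500 mg tablets will be used". The table has five BSA bands, each with a total daily dose and a morning and evening tablet count.

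Section 8.1.5 gives the same 750 mg/m² twice-daily dose and says that the daily total calculated from BSA "will be rounded down to the nearest 500 mg to allow doses using 500 mg pills". It does not refer to the table.

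Section 5.3.2 confirms that the daily total is calculated first and then split in two. It also says that when a reduction is required, "a reduction of at least 500 mg (of the total daily dose) should be implemented", with the example "if treated originally at 2500 mg daily, only 2000 mg daily may be administered if a dose reduction was called for". Section 5.3.1 bases reductions on the current dose and adds: "No dose escalation is permitted for any of the study drugs".

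For temozolomide, Section 5.1.1.1 says "The calculated dose by BSA will be rounded to the closest mg amount permitted within the confines of available pill sizes", while Section 8.2.5 says "The calculated dose by body surface area (BSA) will be rounded down to minimize the number of pills required".

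**The concern.** Both capecitabine instructions concern the same drug, arm, starting dose and tablet size, and both are directive. A table that rounds to the nearest 500 mg must round up for about half of its entries. A rule that always rounds down cannot agree with it there. Two patients of identical BSA could therefore start one tablet a day apart, depending on which section their site or pharmacy used.

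The gap is the size that Section 5.3.2 sets as the minimum reduction for toxicity. It falls only on the experimental arm and could vary by site. Later reductions start from the current dose, and any recalculation after a weight change of 10% or more meets the same two rules again.

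**Working it through.** **Inputs.** Daily dose 1500 mg/m² and the five table rows (Section 5.1.1.1); rounding down to 500 mg (Section 8.1.5); daily total calculated before splitting (Section 5.3.2). BSA is taken to two decimals, matching the table's band limits, so 1.20 to 2.83 gives 164 values.

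**Step 1: reproduce the table.** Calculated dose = 1500 × BSA. Rounded to the nearest 500 mg, this matches the table at 164 of 164 values if exact ties go down. If ties go up it matches at 162 of 164; the two ties are BSA 1.50 (2250 mg) and BSA 2.50 (3750 mg). The table is therefore correct under nearest-500 rounding.

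**Step 2: apply Section 8.1.5.** Dose = 500 × floor(1500 × BSA / 500), compared with the table row by row:

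| BSA band (m²) | Table dose (mg/day) | BSA values that differ | Rounded-down dose there (mg/day) | Count | Gap as % of table dose |
|---|---|---|---|---|---|
| 1.20–1.50 | 2000 | 1.20–1.33 | 1500 | 14 of 31 | 25% |
| 1.51–1.83 | 2500 | 1.51–1.66 | 2000 | 16 of 33 | 20% |
| 1.84–2.16 | 3000 | 1.84–1.99 | 2500 | 16 of 33 | 16.7% |
| 2.17–2.50 | 3500 | 2.17–2.33 | 3000 | 17 of 34 | 14.3% |
| 2.51–2.83 | 4000 | 2.51–2.66 | 3500 | 16 of 33 | 12.5% |

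Total: 14 + 16 + 16 + 17 + 16 = 79, and 79/164 = 48.2%. The gap is 500 mg/day at all 79 values, with the table higher. The other 85 values agree.

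**Step 3: check by hand.** BSA 1.60 × 1500 = 2400 mg, so 2500 mg by the table and 2000 mg by Section 8.1.5. BSA 1.84 × 1500 = 2760 mg, so 3000 mg and 2500 mg.

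**Step 4: dose per m².** Averaged with equal weight over the 164 values, the table delivers 1499 mg/m²/day and rounding down delivers 1367, a ratio of 0.912 (8.8% lower). The lowest rounded-down value is 1500/1.33 = 1128 mg/m²/day.

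**Step 5: other readings of Section 8.1.5.** Rounding each single dose down, instead of the daily total, widens the disagreement to 113 of 164 values (67 by 500 mg/day, 46 by 1000 mg/day). Rounding up disagrees with the table at 84 of 164. Neither removes the conflict.

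**Step 6: share of patients (assumption).** The documents give no BSA distribution. If BSA is normal with mean 1.6 to 2.1 m² and SD 0.15 to 0.30 m², 47% to 50% of Arm A patients would be affected. With SD 0.10 the range is 38% to 59%.

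**Step 7: temozolomide.** Calculated dose = 200 mg/m² × BSA, capped at 400 mg. Because 5 mg capsules are listed, rounding to the closest 5 mg and rounding down to 5 mg differ at 32 of the 164 BSA values, by 5 mg each. All 32 lie among the 80 values below the cap (BSA 1.20 to 1.99). A larger gap would depend on how the aim of limiting pill numbers in Section 8.2.5 is read.

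**The case against.** The strongest reply is that the table is plainly the working instruction. It stands in the Treatment Plan, it is directive, and its tablet counts leave a site nothing to round. Section 8.1.5 is one sentence in the drug formulation and procurement section. Harm needs a pharmacy to work from Section 8 and not Section 5, and the documents neither show nor exclude that. This stands as a reason to expect many sites to follow the table. It does not make the conflict acceptable, because Section 8 is where drug-specific dose details are placed and the protocol sets no order of precedence.

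Other points have some force:

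- The gap equals the minimum toxicity reduction because each is one 500 mg tablet. The example in Section 5.3.2 fits either rule, since rounding down also yields 2500 mg at BSA 1.67 to 1.99. The comparison shows the size of the gap; it is not further evidence of the conflict.
- The starting dose is not fixed for every patient. A weight change of 10% or more triggers recalculation, and the ban on escalation is stated alongside permanent reductions, so whether it bars correcting a rounding choice is open. But a recalculation needs a rounding rule too. The hyperbilirubinemia reductions in Section 5.3.2.2, which are percentages of the starting dose, would carry the difference forward.
- The 79 of 164 counts BSA values, not patients, and the patient share has no source in the documents.
- Temozolomide is a side note and adds no weight to the main point.

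**Conclusion.** The conflict is real and should be fixed. It is an inconsistency between two dosing instructions, not an error of calculation. The two capecitabine rules differ by 500 mg/day, with the table higher, at 79 of 164 BSA values (48%). That count assumes BSA recorded to two decimals and rounding of the daily total, as Sections 8.1.5 and 5.3.2 describe. Any patient percentage rests on an assumed BSA distribution. The temozolomide wording conflict is minor: 5 mg at most under plain rounding. Sample size, event count and power do not depend on either rule. No view is taken on which dose is right.

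**What to change.** Reconcile Section 5.1.1.1 with Section 8.1.5 for capecitabine, and Section 5.1.1.1 with Section 8.2.5 for temozolomide, so that each drug has one rounding rule worded the same wherever it appears. The capecitabine table has rows only for the starting dose level, so the wording should also say whether the rule covers reduced doses. The clinical leads choose the rule. Site pharmacies should be notified when the amendment is issued.

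The cost is amendment wording and a pharmacy memo. There is no statistical cost.
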